Organizational structure of the team	
Translation, Recruitment, Training, and Ethics/Research Committee Approval. Contributions to Data Collection, Analyses, Interpretation, Writing, and Dissemination Activities.
 
CCIHP Site Principal Investigator: [name], MSc Research Assistants (Total = 1)
 
Emory University IRB Approval, Contributions to Data Collection, Analyses, Interpretation, Writing, and Dissemination Activities.
 
Emory University Principal Investigator: [name] Co-Investigator: [name] Consultant: [name]

Setting and location	
Setting. The undergraduate system in Vietnam is a suitable context for adapting the program, given its similarities with the US context where the program originated. Undergraduate study is 4–6 years, with two foundational years and 2–4 years for specialization. Except for political education and national defense, universities design their own curricular and extra-curricular activities and maintain networks through the Ministry of Education and Training (MoET), professional associations, and Youth Union, all potential pathways to bring the program to scale in the future.
 
Study site. The sites for this project are Hanoi Medical University (HMU) and Thang Long University (TLU), both in Hanoi. HMU is a 100-year-old state school with dental, medical, nursing, nutrition, public health, and paramedical/ ophthalmology technical programs. Its 1000 enrolled students are 40% men. TLU is a 24-year-old private university with 15 departments (e.g., math, business administration, social sciences). Its 7000 enrolled students are 45%-50% men. Both schools have provided letters of support for adaptation of the program with their students.

Quantitative Study Population	
Men 18–24 years and identifying as heterosexual or bisexual and enrolled at HMU and TLU as freshmen on 9/1/2019 are eligible.

Recruitment

Study design. Based on learning from the qualitative work, we will conduct a RCT with eligible college men to test the impact of the program on promoting prosocial bystander behavior and preventing sexual violence perpetration, through improvements in the seven knowledge, attitudinal, and emotional mediators over a seven month study period, with a baseline survey and two follow-up surveys 0 and 6 months post-intervention. Figure 1 depicts the basic RCT design.

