Survey sample and power. Men 18–24 years and identifying as heterosexual or bisexual and enrolled at HMU and TLU as freshmen on 9/1/2019 are eligible. According to recent enrollment figures, about 890 men matriculate yearly at HMU and TLU. Given a cooperation rate of 67% in similarly focused research among male Atlanta-based undergraduates,⁶⁸ this pool is sufficient to recruit a sample of 400 freshman men for participation in this study.

We computed the required sample sizes to detect our hypothesized effects with a power of .80. We used a Monte Carlo approach⁹¹ to calculate the required sample sizes 1) assuming an attrition rate of 30%; based on 2) Cohen’s medium-to-large-effect-categorization⁹² with regards to the proportion of the variance accounted for, R², by the model (.13 and .26) using corresponding values for a and b;⁹³⁻⁹⁵ and 2) a desired power level of .80. The computer program, Mplus,⁹⁶ was used to complete the computations.

To recruit students, CCIHP personnel will contact department chairs at each university to discuss the study with them. With their agreement, CCIHP will talk with faculty about the study and ask them to announce it in their classes using a flyer with a brief, standard project description. The department chair will obtain email and phone numbers of students. The team has used this strategy successfully to recruit undergraduates. The study staff will utilize student phone numbers to contact students to make sure they check their emails.

Field Methods

Data collection overview. After consent, participants will be assigned randomly, with an equal allocation to Real-Consent or a health-education

control program, using block randomization with random block sizes. Participants and analysts will be blinded to assignments.

Outcomes will be assessed at baseline, posttest (just after finishing the last module), and six months (Table 2). We will consider confounders and modifiers, like social desirability, emotional adjustment, sensation seeking, sexual behavior, aggressive peers, peer and social network diversity, peer social support, witnessing family violence, family cohesion, and social support (Table 2). Questions will model others in the field.⁶⁸

Table 2. Primary (Behavioral) and Secondary (Knowledge/Attitudinal/Emotional) Outcomes at Baseline, Posttest, and Six-Month Follow-Up				
Construct	Scale	Sample item	#	Resp
Primary Outcomes				

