Bystander self-efficacy	ROLB self-efficacy to intervene in SV ¹⁰¹	When I hear a sexist comment I indicate displeasure	8	1-7
Bystander intervention	ROLB self-behavior subscale ¹⁰¹	walk into my room & roommates are watching porn	5	1-7
Intimate Partner Violence	Revised Conflict Tactics Scale (CTS2) SV ¹⁰²	Used force to make partner have sex	7	1-6
Sexual Violence	Sexual Experiences Survey Rev. (SES-R), SV ¹⁰³	put my penis, fingers, objects into so's butt w/o...consent	8	0-3
Secondary Outcomes (Knowledge, Attitudinal, Emotional Mediators)				
Knowledge of law	Knowledge of legal defs of assault/rape scale ¹⁰⁴	Sex intercourse w/so <16 [is legal if] he/she gives consent	9	T/F
Knowledge of consent	Knowledge of informed consent to have sex ⁶⁸	If a woman dsn't physically resist sex, she has given consent	14	T/F
Norms degrading wn	ROLB other-behavior subscale ¹⁰¹	Rmate suggests...give alcohol to your date to 'loosen her up'	5	1-7
Gender attitudes	Hostility Toward Women Scale ^{105,106}	...many times women flirt w/men just to tease/hurt them	10	T/F
Gender attitudes	Hyper-Gender Ideology Scale short form (HGIS) ¹⁰⁷	If men pay for a date, they deserve smthg in return	19	1-5
Rape attitudes	College Data Rape Attitude & Behavior Survey ¹⁰⁸	...sex jokes and innuendos are only fun & harmless	20	1-5
Rape attitudes	Illinois Rape Myth Acceptance (IRMA) ⁴⁸	Rape happens when a man's sex drive gets out of ctrl	17	1-5
Dating violence attitudes	Attitudes Toward Male Dating Violence Scale ¹⁰⁹	A guy should not insult his girlfriend	39	1-5
Empathy for rape victims	Rape Empathy Scale (RES) ⁵⁴	In general,...rape is not...provoked by the rape victim	19	1-5
Control Variables				
Alcohol use	National College Health Assessment Survey ¹¹⁰	# drinks consumed when last partied	1	#
Sexual behavior	Safe Sex Behavior Questionnaire (SSBQ) ¹¹¹	engage in sex intercourse on the first date	7	1-4
Sexual communication	Communication self-efficacy ¹¹² (to discuss sex)	can discuss...using condoms w/any sex partner	4	1-10
total items and time required			192	42 m

Note. SV = sexual violence; α indicates the reliability of the scale in other samples.

Informed Consent

Assurances, IRB approvals, and oversight: Our ethics protocol will follow WHO guidelines for research on violence against women.¹³¹ Ethical approval will be sought from CCIHP, Emory University, and Georgia State University. Team members have completed certification training in research ethics.

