
Data Management and monitoring
	
Data systems will be designed to handle the concurrent collection, processing, secure storage, and analysis of project data. New data will be aggregated progressively via a web-based data-entry application (REDCap). Each participant will be assigned a unique number identifying him across waves. The web application will transmit data entered by each participant through an encrypted network connection to a centralized database running on a secure network and infrastructure, ensuring secure electronic data movement. A CCIHP programmer will create, and a CCIHP data manager will run, applications for more refined range/ consistency checks in the centralized database. Systematic data collection errors can be identified, resolved, and documented using a workflow module of the REDCap application. Some statistical software can access data in the central database and store derived variables there. For analyses done with external statistical software, de-identified data will be extracted and held on HIPAA compliant secure networks and computing workstations.

Plans for analysis

[figure not shown]

Descriptive analyses. We will perform univariate analysis of all demographic, screening, mediating, outcome, and control variables for the program and the health-education control groups, individually and combined, to explore distributions, outliers, and missingness. The associations between individual pairs of variables will be examined. Baseline differences on these variables between the program and health-education control condition will be tested. The psychometric properties of the various instruments will be assessed and confirmed.

Intent-to-treat analysis. To assess our aims based on the randomization scheme,¹¹⁴ we will perform mediation analyses via path analysis.^{115,116} Namely, we will assess first whether, relative to men randomized to the health-education control group, men randomized to the program will have improved mediating outcomes (H1). With reference to Figure 2, each of these relationships is represented by path a, or the direct effect of treatment on the mediator. Testing the significance of each path allows us to assess the impact of the program on each mediator. The standardized effect coefficients will serve as effect size measures of the treatment to mediator relations.

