We will test the robustness of the results obtained by investigating potential confounders of paths a and b, which may result in biased estimates. Figure 3 shows how confounders may affect the estimates of relationships between 1) treatment and mediator with tm_1 and tm_2 , and 2) mediator and outcome with mo_1 and mo_2 , which may be biased as a result of omitted or confounding variables.^{117,119} As there will be randomization of the program treatment but not of the mediator variables, most confounders on the treatment-to-mediator relation should be eliminated. Still, we will, perform a balance check on randomization using the control variables listed in Table 5. If imbalance on certain variables is detected, those variables may be controlled for when estimating path a, the program treatment-to-mediator relation. We also will assess the sensitivity of the results to the potential confounders on the mediator-to-outcome relation, path b, using a propensity score approach.^{120,121} The propensity score, or the probability that an individual receives a specified level of the mediator, given a set of observed covariates chosen from Table 5, will be estimated and used as a covariate in the mediation model to estimate path b. The results will be compared to those without any adjustment to detect if possible biases exist due to omitted observed confounders, and if they do, what the directions and magnitude are.

We will perform the intent-to-treat analyses using the software program, Mplus.⁹⁶

Supplemental analyses in the program group. We will conduct several analyses in the program group to assist with the interpretation of findings from the intent-to-treat analyses. First, to gauge possible dose-response relationships between engagement with the program, such as total contact time over the six-session program, and individual post-treatment mediator and outcome variables, we will examine their partial correlations for participants assigned to the program group, adjusting for their corresponding baseline values.¹²² Second, we will assess differential program impact by examining differences in pretest-posttest change scores in mediator and outcome variables across socio-demographic characteristics, such as age, and risk groups, such as alcohol use.

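### Pretest-posttest change in self-reported perpetration, within the program group and with no recall period stated, cannot be read as program impact

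*Combined protocol and SAP*

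**What the plan says.** Under Quantitative Study Design, Recruitment (Study design), the trial runs "over a seven month study period, with a baseline survey and two follow-up surveys 0 and 6 months post-intervention". Field Methods (Data collection overview) puts every outcome at every wave: "Outcomes will be assessed at baseline, posttest (just after finishing the last module), and six months (Table 2"). Table 2, titled "Primary (Behavioral) and Secondary (Knowledge/Attitudinal/Emotional) Outcomes at Baseline, Posttest, and Six-Month Follow-Up", lists two perpetration measures among the primary outcomes: "Revised Conflict Tactics Scale (CTS2) SV" (7 items, responses 1-6) and "Sexual Experiences Survey Rev. (SES-R), SV" (8 items, responses 0-3). The table gives construct, scale, sample item, item count and response range. Neither it nor the surrounding text gives a recall period at any wave.

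Plans for analysis (Supplemental analyses in the program group) opens with: "We will conduct several analyses in the program group to assist with the interpretation of findings from the intent-to-treat analyses". Its second analysis is the one at issue: "we will assess differential program impact by examining differences in pretest-posttest change scores in mediator and outcome variables across socio-demographic characteristics". It extends to risk groups and names alcohol use as an example. Nothing exempts the perpetration scales.

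**The concern.** A score for past acts means little until the period it covers is known. Attitude and knowledge scales describe the respondent now, so a change from baseline to a survey straight after the last module can be interpreted. A perpetration score looks backwards. At zero months after the intervention, any recall period consists of the program weeks plus time before baseline, so the behaviour the program is meant to change afterwards has not yet had time to occur.

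The analysis has no control arm, so an artefact of the reporting period cannot cancel against a comparison group. Comparing subgroups does not cancel it either, because the artefact grows with the underlying rate. A higher-risk group could appear to benefit more from a program that does nothing, or a real benefit could be hidden because most of the acts counted precede the program.

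**Working it through.** **Inputs from the plan.** Study length is 7 months and the last survey is 6 months post-intervention (Recruitment). The sample is 400 with 30% attrition (Survey sample and power). Men's reported sexual violence perpetration is 0.2%, with no recall period given (Background, on engaging men). The plan has no figure of its own on this point to reproduce.

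**Assumptions.** Constant rate of acts, no program effect unless stated, a six-month baseline period, and six-month prevalences p of 5%, 10% and 20% alongside the documents' 0.2%. None of the recall periods below is in the documents.

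**Step 1, spacing.** 7 − 6 = about 1 month from baseline to posttest.

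**Step 2, posttest period shorter than baseline period.** One-month prevalence = 1 − (1 − p)^(1/6).

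| Six-month rate | One-month rate | Fall, points | Relative fall |
|---|---|---|---|
| 0.2% | 0.03% | 0.17 | 83% |
| 0.8% | 0.13% | 0.67 | 83% |
| 5% | 0.85% | 4.15 | 83% |
| 10% | 1.74% | 8.26 | 83% |
| 20% | 3.65% | 16.35 | 82% |

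The false difference in impact between a 20% group and a 5% group is 16.35 − 4.15 = 12.2 points. Between a 0.2% group and a group at four times that rate (0.8%) it is 0.67 − 0.17 = 0.5 points. With a two-month gap the relative fall, 1 − [1 − (1 − p)^(2/6)]/p, is still 64-67%.

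**Step 3, equal periods of W months at both waves.** The expected change under no effect is zero. The share of the posttest period lying before baseline is (W − 1)/W: 67% for W = 3, 83% for W = 6 and 92% for W = 12. With W = 6, even a program that stopped all acts from its first day would lower the expected number of acts only from 6 to 5 rate-months, or 17%.

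**Step 4, equal periods of about one month.** These do not overlap, but they still contain only program time and leave few events. Completers per arm are 400 × 0.70 / 2 = 140. Expected men reporting any act are 140 × 0.0085 = 1.2, 140 × 0.0174 = 2.4 and 140 × 0.0365 = 5.1 at p = 5%, 10% and 20%, and 0.05 at 0.2%.

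**Step 5, the six-month survey.** A 12-month period there is 5/12 (42%) pre-baseline, 1/12 (8%) in-program and 6/12 (50%) post-program. Suppose the program halves the rate after it ends. Control men then have 12 rate-months and program men 6 + 6 × 0.5 = 9. The risk ratio is [1 − (1 − p)^1.5] / [1 − (1 − p)^2] = 0.76, 0.77 and 0.79 for p = 5%, 10% and 20%. With a six-month period it is [1 − (1 − p)^0.5] / p = 0.51, 0.51 and 0.53.

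For a simple two-proportion test with 140 per arm and two-sided 5% (assumed), moving from the six-month to the 12-month period lowers power from 34% to 16% at p = 10%, and from 59% to 27% at p = 20%. At 0.2% power is about 5% or less with either period. The plan tests indirect effects by bootstrap, so these powers only illustrate the dilution.

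**The case against.** The strongest reply is that unequal recall periods are conjecture. The instruments are not in the documents and may carry a fixed period. With equal periods and a constant rate, the expected change under no effect is zero. That stands. A reader might infer that the observed change will reflect the reporting period rather than the program, and the documents do not support so firm a statement. Equal periods do not rescue the analysis, however: steps 3 and 4 show that they give mostly repeated pre-baseline acts or very few events.

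A second reply concerns weight. The analysis is supplemental and limited to one arm. A reader might infer that the tests of H1-H3 are biased too. They are not: the Intent-to-treat analysis compares randomized arms surveyed on the same schedule, so any period common to both gives zero expected difference under the null. An over-long period would dilute a true effect there, and an unstated one leaves the H3 outcome incompletely defined.

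A third reply is that the absolute size may be tiny. At 0.2% it is, although that figure comes from a different setting and the documents themselves warn of underreporting.

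Two further inferences lack support. Table 2 gives response ranges but does not say that the codes are capped counts. Adjusting for baseline in the dose-response correlations is not a fault in itself, since a covariate need not share the outcome's recall period.

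**Conclusion.** The point holds for one stated rule: pretest-posttest change in CTS2 SV and SES-R within the program group cannot be separated from the reporting period and should not be read as program impact, overall or by subgroup. This follows from the timing of the posttest and does not depend on which recall period the instruments use. The direction and size of any artefact do depend on it. With six-month then one-month periods and a constant rate, the relative fall is about 82-83%, and the absolute fall runs from about 0.2 to 16 points across six-month rates of 0.2% to 20%. The one-month gap is inferred, and the 5-20% rates are assumed. The randomized comparisons are not biased under the null. Their exposure is dilution, and only if the recall period reaches back before randomization, that is, beyond about seven months at the last survey.

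**What to change.** In Plans for analysis (Supplemental analyses), remove CTS2 SV and SES-R from the pretest-posttest change scores and examine them at the six-month survey. Preferably do this as an arm-by-subgroup comparison using both arms, adjusted for baseline. Within-program change to six months would still lack a control, and for freshmen a six-month baseline period may reach into time before university. Keep pretest-posttest change for the scales that have no recall period.

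In Field Methods and Table 2, state one fixed period for both scales: the past six months, with the calendar start date shown on screen, at baseline and at the six-month survey, in both arms. Do not anchor it to the posttest survey, because men who missed that survey would have no anchor date. Report any perpetration data collected at posttest descriptively only.

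The cost is the wording of two item stems in an online survey and a short change to the analysis text. No pretest-posttest change in perpetration would be reported, and published scoring tied to another recall period may not apply directly.

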The Legal Framework in Vietnam Favors Sexual Violence Prevention

In the context of social norms and kinship practices favoring male dominance, the State has pursued legal reforms to promote gender equality, penalties for gender-based violence, and violence prevention. The Law on Marriage and Family in 1986 gave men and women equal rights in marriage, and the Law on Gender Equality in 2006 sought to eliminate gender discrimination and to curb differential rights based on gender.³⁶⁻³⁸ The Penal Code of 1989 defined penalties for acts of sexual violence.^{39,40} Rape was defined legally as an act committed by someone who, through violence or its threat, or by using the victim’s helplessness or other means, forces the victim to have sexual intercourse against her will. Rape carries a punishment of imprisonment for two to seven years. Convicted offenders are barred from certain jobs or positions of responsibility for one to five years. Terms of up to 20 years or even life imprisonment could be imposed when victims suffer grievous bodily harm, perpetrators are known HIV carriers, or victims die or commit suicide because of the rape.⁴¹ A 2007 law codified definitions of physical, psychological, sexual, and economic violence as a step to prevent these forms of violence.^{42,43}

	
Preventing Sexual Violence Must Engage Men
 
Despite legal reform, sexual and other forms of violence against women persist in Vietnam.^{37,43} In our research outside of Hanoi, men have discounted, excused, or denied many acts of violence.⁴⁴ As a result, men’s reported rates of sexual violence perpetration (0.2%) are lower than women’s reported rates of victimization (12.0%).¹⁵ Thus, prevention work with men is critical to create an environment where women’s bodily integrity and freedom from violence are possible.⁴⁵ Yet, young men often are difficult to reach^{46,47} and resist programs that target sexual violence, not seeing themselves as potential perpetrators.⁴⁸ Limited data also suggest that the behavior of bystanders, or witnesses of sexual violence, is gender-specific.⁴⁹ Although evidence from rigorous evaluations is limited,⁵⁰ prevention with men that integrates a bystander framework is a way to target attitudes and behaviors while decreasing resistance to participation⁵¹⁻⁵³ because men are treated as the “allies” of women.⁵⁴

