Analytic issues and strategies. 1) We note and will address relevant analytical issues in this application. Reports of sexual violence. While men may systematically underreport SV perpetration, our own research suggests that men's reported rate of IPV perpetration (37%) can be similar to women's

	
reported rate of IPV exposure (43%) with appropriate quality controls.^{15,123} Our decision to use an online computer-assisted-self-interview platform should enhance disclosure by maximizing the possibility for privacy during the interview. Differential non-participation/attrition. We will explore the differential non-participation/attrition of men to assess for risk of response bias. With the baseline screening, socio-demographic, and other control data, we will model the response probability and use the estimated response probability to compute weights to correct for unit nonresponse using the covariates in Table 5. Estimates on the various outcomes before and after reweighting, and under different assumptions with respect to missing data, will be compared. Item non-response. For covariates with a non-response rate of $\geq 5\%$, we will test for differences between responders and non-responders. We will compare non-responders and responders and may use multiple imputation, assuming the data are missing at random, to fill in the missing values.¹²⁴⁻¹²⁶ Noncompliance. As some participants in the program group may not receive the program, we will estimate complier-average causal effect (CACE) of the program by estimating two latent classes of compliers and non-compliers using engagement of the program as well as covariates and control variables.^{127,128} The CACE results will afford comparisons with and robustness assessment of those of the intent-to-treat analyses, and allow an examination of potential predictive factors of engagement with the program and its intervention implications.¹²⁹ Outliers. We will assess the sensitivity of the results to outliers. We will exclude univariate outliers if their z scores exceed ± 3. Multivariate outliers will be diagnosed using Mahalanobis distance and excluded if $p < .0001$. Results from the complete and reduced data sets will be compared. Convergence issues and improper solutions. We will assess the causes of convergence issues and improper solutions when running the path analyses, such as model misspecification, non-identification, and collinearity—and we will remediate by specifying suitable start values and model re-specifications.¹³⁰ Generalizability. To simplify logistics and enhance feasibility of the RCT, our study sites are two universities. This strategy does not permit generalization to college men in Vietnam, but the two sites enhance the overall diversity of the sample. We will describe our sample clearly to help others understand the young men to whom study findings may be relevant and generalizable.

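### The outlier check exempts no variable, so on the two sexual-violence outcomes its reduced data set drops men because they reported violence, and the comparison is hard to read for H3.

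*Combined protocol and SAP*

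**What the plan says.** The rule is in the quantitative Plans for analysis, under Analytic issues and strategies, in the item on outliers. It reads "We will exclude univariate outliers if their z scores exceed" ±3, followed by "Multivariate outliers will be diagnosed using Mahalanobis distance and excluded if" p < .0001. It is framed as a sensitivity assessment: "Results from the complete and reduced data sets will be compared". The item does not list the variables covered, exempts none, and does not say how a difference between the two sets of results should be read.

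Table 2 lists CTS2 sexual violence (7 items, coded 1–6) and SES-R sexual violence (8 items, coded 0–3) among the four primary outcomes. They are the perpetration measures behind H3. No scoring rule is given for them, and no count, ordinal or zero-inflated model is planned. The Intent-to-treat analysis item takes the standardized indirect effect as the effect size. Data Management and monitoring separately plans "refined range/ consistency checks in the centralized database".

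On rates, the Background says that in earlier work men's "reported rates of sexual violence perpetration (0.2%) are lower than" women's "reported rates of victimization (12.0"%). The item on reports of sexual violence says men's "reported rate of IPV perpetration (37%) can be similar to" women's "reported rate of IPV exposure (43%) with appropriate quality controls". That second pair concerns intimate partner violence, not sexual violence specifically.

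**The concern.** A z cut-off of 3 is built for roughly symmetric scores, where extreme values are rare and may be errors. On a perpetration scale with most men at the floor, the men beyond the cut-off are those who reported the behaviour the trial aims to reduce. Impossible values should already have been caught by the range checks, so what remains to be removed is mostly in-range answers. The reduced data set is then selected on the outcome.

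If the program works, the control arm has more reporters, so more deletions fall there and the raw contrast shrinks. A reader could conclude that an H3 effect rests on outliers when the analysis has simply deleted the events. Equally, a reader could be reassured by a stable standardized effect that is stable only because the outcome SD shrank as well.

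**Working it through.** The plan gives no deletion count and no sexual-violence rate for this sample, so there is no figure of its own to reproduce.

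**Inputs from the documents.** 400 men, equal allocation, 30% attrition: 400 × 0.70 = 280 completers, 140 per arm. Score ranges from Table 2: SES-R 8 × 3 = 24, so 0–24; CTS2 7 × 1 to 7 × 6, so 7–42. R² = .13 from the power paragraph.

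**Assumptions.** The R² of .13 is applied to path a: r = √.13 = 0.36, and d = 2r/√(1 − r²) = 0.77 SD. Path b is a log-odds of −1.0 per SD of mediator. Reporters' scores are geometric, with mean 2 or 4 (SES-R) or mean excess over the floor of 3 or 6 (CTS2). z is computed on both arms pooled. The rates are a range, not estimates.

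**Benchmark.** For a normal variable, 0.27% lies beyond |z| = 3, which is 0.0027 × 280 ≈ 0.8 men.

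**Lowest rate.** At 0.2%, 280 × 0.002 = 0.56 reporters are expected. H3 cannot be analysed at that rate with or without the rule.

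**Sum scores** (linear path model, 3,000 simulated trials per cell). The 10.3% row is 12.0% × 37/43, which supposes that men disclose sexual violence in the ratio the plan quotes for partner violence.

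| Control vs program | Reporters removed | Total score removed | Raw ab, reduced ÷ complete | Standardized ab |
|---|---|---|---|---|
| 8% vs 4% | 38–42% | 66–70% | 0.32–0.35 | shrinks 6–10% |
| 10.3% vs 5.3% | 32–34% | 59–64% | 0.38–0.43 | shrinks 2–4% |
| 12% vs 6% | 29–30% | 55–60% | 0.42–0.48 | within about 1% |
| 20% vs 11% | 18% | 40–46% | 0.58–0.64 | grows 6–7% |
| 37% vs 23% | 8–9% | 22–28% | 0.76–0.82 | grows 9–10% |

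Every row loses 6–8 of the 280 men. No non-reporter was ever removed on the outcome. At 8% vs 4%, about 4.7 of the men removed are controls and 2.3 are in the program arm. A repeat for SES-R with 1,500 trials per cell agreed within simulation error (at 8% vs 4%: 40–43% of reporters removed, raw ab ratio 0.33–0.36).

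**Why the two effect measures part.** Standardized ab is raw ab × SD(arm)/SD(outcome). For SES-R with mean 2 at 8% vs 4%, it goes from −0.072 to −0.065, a ratio of 0.90, while raw ab keeps about 0.35. The outcome SD has therefore fallen to about 0.35/0.90 = 0.39 of its value.

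**Significance.** With 400 trials and 500 bias-corrected bootstrap resamples at 8% vs 4%, ab was significant in the complete data in 360–365 trials. The z rule lost significance in 16–18% of these, against 1–2% when the same number of men was deleted at random. At 10.3% vs 5.3% the figures were 8–9% against 0.5–1.6%.

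**Yes/no scoring** (not stated in the plan). A reporter has z = √((1 − p)/p), which exceeds 3 only if p < 0.10. With 280 men, 27 reporters give z = 3.06 and all are deleted; 28 give z = 2.995 and none is. The indirect effect then cannot be estimated in 99% of trials at 8% vs 4%, 88% at 10.3% vs 5.3%, 66% at 12% vs 6%, and under 1% at 20% vs 11%.

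**Mahalanobis, p < .0001.** This is generally milder and depends on the variable set, which the plan does not list. With one violence scale and one or seven mediators it removes 19–26% of reporters at 8% vs 4%, 11–17% at 12% vs 6%, and 2–4% at 37% vs 23%. With fifteen variables, of which one is a violence scale, about 15% are removed at a pooled rate of 6%. With both violence scales among the fifteen, 24% are removed at a pooled rate of 8%.

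**The case against.** The strongest reply is that nothing planned is displaced. The complete-data result is kept, and showing that a result rests on a handful of men is what an outlier comparison is for. The plan's own effect size moves by about 10% or less at every rate tried; the large change is in the raw effect, and it is largest at the lowest rate simulated. Any deletion of extreme scorers costs more significance than random deletion, so that benchmark is lenient. All rates and score shapes are assumed. The total loss of reporters needs yes/no scoring, while Table 2 shows graded responses. The descriptive step would reveal the floor before anyone read the comparison. Finally, an in-range answer can still be careless, and range checks will not catch it.

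Most of this stands, and it sets the weight of the point: a sensitivity analysis on assumed rates, with the yes/no case as a side branch. It does not rescue the rule for these two scales. Selection on the outcome appears at every sum-score rate tried. The z cut-off cannot tell a careless answer from a truthful report of violence. The stable standardized effect comes from two quantities shrinking together, so it is not evidence of robustness. Seeing the floor in the descriptive tables does not change what the rule deletes.

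**Conclusion.** The concern holds, with modest weight. As written, the exclusions reach both sexual-violence primary outcomes, and on floor-heavy scores the reduced data set is selected on the event under study. The main H3 analysis is not biased by this; the planned comparison is hard to interpret. With sum scores the comparison loses 6–8 of 280 men. Raw ab keeps 0.32–0.35 of its value at 8% vs 4%, rising to 0.76–0.82 at 37% vs 23%, while standardized ab changes by about 10% or less in either direction. These sizes rest on assumed reporting rates, severity distributions and path strengths. That most men score at the floor is itself an inference, supported by the low male reporting rate in the Background. Only under yes/no scoring with a pooled rate below about 10% does the check fail outright.

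**What to change.** In the outlier paragraph:

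- List the variables to which the z and Mahalanobis exclusions apply, and exempt SES-R and CTS2 sexual violence from both.
- For these two outcomes, remove only impossible values found by the planned range checks, or records failing quality checks defined in advance without reference to the outcome.
- Replace the deletion check for each with one sensitivity model that keeps every reporter and retains severity, either count or ordinal. An any-versus-none analysis is an optional addition. An ordinal logit (0, 1–2, 3 or more) with arm and mediator converged in 59–60 of 60 simulated trials at both 8% vs 4% and 10.3% vs 5.3%, a small test but an encouraging one.
- State that the complete-data result is primary, and report exclusions by arm for the other variables.

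The cost is one SAP paragraph and one extra sensitivity model per outcome, plus the work of defining the outcome-blind quality checks, which the protocol does not yet contain. No new data are needed. The downside is that the linear path result for these two outcomes is no longer tested by deleting its extreme scorers.
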